Full study protocol and statistical analysis plan

Official Title of the study:

Analysis of some heavy metals and some vitamins levels in maternal samples, fetal samples and breast milk for fetal growth restriction.

Date of the document:

May 2020.

Contents:

1. Participant Flow
2. Baseline Characteristics
3. Outcome Measures
4. Endpoints of the study
5. Limitations and Strengths
6. Certain Agreements
7. Results Point of Contact

1. Participant Flow

Recruitment Details

This observational case-control study will be conducted at the Department of Obstetrics and Gynecology, Cengiz Gokcek Public Hospital, Gaziantep, Turkey, between May 2020 and February 2021. The protocol was approved by the Ethics Committee for Clinical Research of Gaziantep University (reference no: 2020/131). The study strictly will be adhered to the principles of the Declaration of Helsinki. All subjects will be included in the study gave oral and written informed consent. 110 women were enrolled in the study in two groups.

Pre-assignment Details

The authors first will be assessed the recruited people to ensure meeting the inclusion and exclusion criteria. The inclusion criteria will be made according to the official documents.

Arm/Group Information *

There are two groups in the study.

Arm/Group Title *

Fetal growth restriction group

Control group

2. Baseline Characteristics

To detect significant difference between groups according to lead levels with a moderate effect size (Cohen's $d=0.6$), minimum required sample size was estimated as 45 for each group ($\alpha=0.05$, $1-\beta=0.80$). Power analysis was performed by using G power package version 3.1. Kolmogorov Smirnov and Shapiro Wilk tests will be used to test the normal distribution of data. For comparing groups (FGR/control) the student t-test will be used for variables that have a normal distribution, and the Mann Whitney U test will be used for variables that have not a normal distribution. The ROC analysis will be applied for the determination of cut-off point for variables. Moreover, Spearman correlation test will be used for the relationship of between variables. SPSS for Windows 22.0 and Medcalc programs will be used for statistical analysis. $p<0.05$ will be accepted as statistical significance.

3. Outcome Measures

Primary Outcome Measures : tin (Sn), manganese (Mn), Vanadium (V), Magnesium (Mg), cobalt (Co), nickel (Ni), arsenic (As), chromium (Cr), cadmium (Cd), lead (Pb), mercury (Hg), antimony (Sb), aluminium (Al), zinc (Zn), copper (Cu), selenium (Se), iron (Fe), vitamin D, vitamin A, vitamin B12 and folate concentrations

Secondary Outcome Measures: composite neonatal outcome (infant weight at delivery, placental weight, neonatal intensive care unit hospitalization, and APGAR scores)

Tertiary Outcome Measures: obstetric ultrasound/doppler examination and fetal-maternal assessment

4. Endpoints of the study:

The primary outcome in these analyses will compare tin (Sn), manganese (Mn), Vanadium (V), Magnesium (Mg), cobalt (Co), nickel (Ni), arsenic (As), chromium (Cr), cadmium (Cd), lead (Pb), mercury (Hg), antimony (Sb), aluminium (Al), zinc (Zn), copper (Cu), selenium (Se), iron (Fe), vitamin D, vitamin A, vitamin B12 and folate concentrations in FGR group and control group.

5. Limitations and strengths:

Our study has some strengths. These metals will be measured blood, urine and hair samples. So, these measurements may not reflect the metals exposure levels only recent exposure and will reflect before and during pregnancy.

6. Certain Agreements

This work will be supported by the Scientific Research Project Fund of Yozgat Bozok University.

7. Results Point of Contact

Corresponding Author: [name], Department of Obstetrics and Gynecology, Cengiz Gokcek Women's and Children's Hospital, Gaziantep, Turkey, [contact]

Address: [name]

GSM: [contact]

[contact]

[contact]

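### Vitamin D is compared without allowing for season of sampling in a study that spans summer and winter; this costs precision, and could bias the result if the groups accrue unevenly

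*Combined protocol and SAP*

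**What the plan says.** Section 1 (Recruitment Details) describes the design and dates: "This observational case-control study will be conducted at the Department of Obstetrics and Gynecology", "between May 2020 and February 2021". That is 10 calendar months, including all of June to August and of December to February. The dates are given for conduct of the study; reading them as the enrolment window rests on the heading they stand under. The same paragraph reports 110 women enrolled in two groups, without giving the split.

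The only selection step described is under Pre-assignment Details: "The authors first will be assessed the recruited people to ensure meeting the inclusion and exclusion criteria". Nothing links the timing of control sampling to that of case sampling.

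Section 4 makes vitamin D part of the primary comparison: "vitamin D, vitamin A, vitamin B12 and folate concentrations in FGR group and control group". It is one of 21 analytes (17 elements and 4 vitamins).

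The test is in section 2: "For comparing groups (FGR/control) the student t-test will be used for variables that have a normal distribution", with the Mann-Whitney U test otherwise. ROC cut-offs and Spearman correlations are the only other analyses. No covariate model or stratification is planned, and recording of the sampling date is not mentioned.

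**The concern.** Vitamin D status depends on sun exposure and so can be expected to vary over the year. This is general subject knowledge, not something the documents state. A pooled two-sample test leaves that variation in two places.

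First, it stays in the error term. Even with identical accrual in the two groups, seasonal spread widens the standard error of the group difference, although a recorded sampling date could remove it.

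Second, there is no randomisation to balance sampling month between the groups. If one group contains more women sampled in the high season, part of the observed vitamin D difference is a difference in sampling time, and the planned test cannot tell the two apart.

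The first effect does not depend on any imbalance. The second depends on it entirely.

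**Working it through.** **The plan's own figure.** Section 2 sizes the study "according to lead levels with a moderate effect size", Cohen's d = 0.6, with alpha 0.05 and power 0.80, and "minimum required sample size was estimated as 45 for each group". A two-sided two-sample t-test with equal groups (noncentral t) needs 44.59, rounded up to 45. The figure reproduces. It concerns lead and is not in dispute.

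**Inputs**
- From the documents: alpha 0.05, and 110 women in total.
- Assumed: 55 per group (110 / 2); two seasons, half of all samples in each; a difference s between high and low season of 0.5, 0.8 or 1.0 within-season SD.
- Varied: the imbalance m, meaning the difference between groups in the share sampled in the high season (0, 10, 20 or 30 points).

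**Step 1: precision under balanced accrual.** A two-level season with an even split adds variance s²/4, in units of the within-season variance.
- s = 0.5: 1 + 0.25/4 = 1.06
- s = 0.8: 1 + 0.64/4 = 1.16
- s = 1.0: 1 + 1.00/4 = 1.25

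Ignoring season therefore inflates the variance by 6% to 25%. Put the other way, a season term is worth about 6% to 25% more women. For scale only, take the plan's d = 0.6 as a within-season effect (it was set for lead, not vitamin D), so that d becomes 0.6/√(1 + s²/4):

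| s | Power, 45 per group | Power, 55 per group |
|---|---|---|
| no seasonal variance | 80% | 88% |
| 0.5 | 78% | 86% |
| 0.8 | 74% | 83% |
| 1.0 | 71% | 80% |

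**Step 2: false positives under uneven accrual, no true difference.** The group means differ by s × m. With high-season shares of 0.5 ± m/2, the standardised shift is d = s·m / √(1 + s²·p(1−p)), where p = 0.5 + m/2. The rejection probability comes from the noncentral t with 108 degrees of freedom and noncentrality d·√(55/2).

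Worked example, s = 1.0 and m = 0.20: p(1−p) = 0.6 × 0.4 = 0.24; d = 0.20/√1.24 = 0.180; noncentrality = 0.180 × 5.244 = 0.94; rejection rate 15%.

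This formula lets the season counts vary by chance around the expected share. A simulation with the counts held fixed (20,000 runs per cell) gives somewhat lower rates, so both are shown. Whole-number counts make the 10- and 30-point cells of the simulation 5/55 and 17/55, that is 9 and 31 points.

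| Imbalance | Formula, s = 0.5 / 0.8 / 1.0 | Fixed counts, s = 0.5 / 0.8 / 1.0 |
|---|---|---|
| 10 points | 5.7% / 6.7% / 7.5% | 5.2% / 5.0% / 4.5% |
| 20 points | 8% / 12% / 15% | 7% / 10% / 13% |
| 30 points | 12% / 21% / 29% | 11% / 21% / 28% |

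Taking both models together, the rate is about 5-8%, 7-15% and 11-29%. With exactly balanced counts the unadjusted test is conservative, at 2.8% to 4.5% for s = 0.5 to 1.0.

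**Step 3: the same data with a season term.** In the fixed-count simulation, a linear model with group and a two-level season term rejected in 4.7% to 5.3% of runs in every cell, whatever the imbalance.

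**The case against.** A reader might infer that the vitamin D comparison cannot distinguish growth restriction from sampling month. The documents do not support that. It is true only if the groups are sampled at different times, and nothing is reported on accrual by month. It would also be tempting to argue that cases arrive sporadically while controls can be filled quickly in a block. The documents say nothing about arrival rates or the order of enrolment, so their silence leaves imbalance possible and does not make it likely. With balanced accrual only precision is lost, and a 10-point imbalance barely moves the error rate. These objections stand, and they limit the bias part to a conditional statement.

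It also stands that every seasonal input is assumed, that vitamin D is one of 21 primary analytes, and that the study was sized on lead with 110 women against the 90 required. No effect on the other 20 analytes is shown.

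One might add that season is just one covariate among many in a plan with no adjustment at all. That is partly fair, since a single covariate model could serve several purposes. But a list of maternal characteristics need not include sampling date, which is a property of the recruitment window. The precision argument is untouched by any of these objections.

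**Conclusion.** The point holds as an inexpensive improvement to one primary comparison. It is not a demonstrated bias. The window, the primary status of vitamin D and the absence of any provision for season are all plain in the text. What is certain in direction is a loss of precision if vitamin D varies by season. Inflation of the false-positive rate arises only if accrual is uneven, and it becomes material from about a 20-point imbalance upward. Both sizes rest on the assumed 0.5 to 1.0 SD seasonal difference, the even season split and 55 women per group. Smaller seasonal differences would give smaller effects.

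**What to change.** 1. In section 2, compare vitamin D between groups with a linear model (log scale if skewed) containing group and one two-level season-of-sampling term. Alternatively, use a Mann-Whitney test stratified by season (van Elteren). Define the two seasons by calendar dates before the data are examined.
2. State that the sampling date is recorded, and report the number of women per group by season.
3. If enrolment is still open, add to section 1 that controls are drawn over the same period as cases. Strict month matching is not needed, because the season term alone brings the error rate back to about 5% in the two-season model above.

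The cost is about one degree of freedom, recording one date per woman, and a few sentences of text. A separate term for each of the 10 months would use nine degrees of freedom in 110 women, so the two-level term is preferable. If enrolment is already complete, as the past-tense count of 110 women may suggest, items 1 and 2 remain feasible wherever sampling dates can be retrieved.

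### The plan states no control of confounding for the primary FGR-versus-control comparison of 21 analytes, so as written it supports only a crude difference in levels

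*Combined protocol and SAP*

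**What the plan says.** Section 1 (Recruitment Details) gives the design: "This observational case-control study will be conducted at the Department of Obstetrics and Gynecology". It also says that "110 women were enrolled in the study in two groups", without giving the split. On eligibility, Pre-assignment Details says only that "The inclusion criteria will be made according to the official documents"; no criteria are reproduced.

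The analysis is in section 2. For the group comparison, "For comparing groups (FGR/control) the student t-test will be used for variables that have a normal distribution". Where that condition fails, the plan switches to a rank test: "the Mann Whitney U test will be used for variables that have not a normal distribution". Two further analyses are named: "The ROC analysis will be applied for the determination of cut-off point for variables", and "Spearman correlation test will be used for the relationship of between variables". Apart from the normality tests, that is the whole plan. Although section 2 is headed Baseline Characteristics, it lists no baseline variable.

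Section 4 applies the group comparison to 17 elements and 4 vitamins, 21 analytes in all. Section 5, on limitations and strengths, gives only a strength: the samples are said to capture exposure before as well as during pregnancy.

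**The concern.** Nothing in a case-control design balances maternal factors between the groups, and no analysis in the plan carries a covariate. If a maternal factor differs between FGR and control women and is related to an analyte, the test can be significant although the groups do not differ beyond that factor. A larger sample does not help: the bias stays the same and is detected more often.

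Only analytes related to an imbalanced factor are affected, and the documents do not show how many that is. At stake is any statement that goes beyond a crude difference in levels. The plan does not say that its conclusions will stop there. ROC cut-offs on raw levels are a legitimate separate use and are not questioned here.

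**Working it through.** **The plan's own figure.** With d = 0.6, two-sided alpha 0.05 and equal groups, the noncentrality of the t-test is 0.6 × √(45 × 45 / 90) = 0.6 × 4.743 = 2.846 on 88 degrees of freedom. Power is 0.804, so the stated 45 per group is reproduced. The one-sided version needs 36, so the stated figure is two-sided. It is for an unadjusted comparison with no covariate term.

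**Reading the text.** Neither matching, restriction on maternal factors, stratification, regression nor a covariate list appears anywhere. Spearman correlation between pairs of variables is not an adjustment. If controls were individually matched under the unseen eligibility documents, the t-test and Mann-Whitney test would still treat the groups as independent.

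**Illustration of size.** From the plan: 45 per group and the total of 110. Assumed: the imbalance, the correlation and the split of the 110. With within-group SDs of 1 and no group difference beyond the factor,

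- bias = imbalance (SD) × within-group correlation with the analyte;
- noncentrality = bias × √(n₁n₂/(n₁+n₂)), where the root is 4.743 for 45:45, 5.244 for 55:55 and 5.157 for 45:65.

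For example, 0.5 × 0.4 = 0.20, and 0.20 × 4.743 = 0.949.

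| Imbalance × correlation | Bias (SD) | 45:45 | 55:55 | 45:65 |
|---|---|---|---|---|
| 0.2 × 0.1 | 0.02 | 5.1% | 5.1% | 5.1% |
| 0.5 × 0.2 | 0.10 | 7.6% | 8.2% | 8.0% |
| 0.5 × 0.4 | 0.20 | 15.5% | 18.0% | 17.6% |
| 0.75 × 0.4 | 0.30 | 29.1% | 34.5% | 33.5% |

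Entries are rejection rates of the two-sided 5% t-test. The Mann-Whitney test on shifted normal data (20,000 simulations) behaves alike: 4.8%, 7.6%, 15.3% and 28.1% at 45 per group, and 5.1%, 7.9%, 17.1% and 32.5% at 55.

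**What adjustment achieves.** These are simulated rejection rates (40,000 runs) from a regression on group plus the one factor, shown as 45 / 55 per group, with covariate reliability assumed.

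| Reliability of the covariate | 0.5 × 0.4 | 0.75 × 0.4 |
|---|---|---|
| 1 (no error) | 5.0% / 5.1% | 5.0% / 4.9% |
| 0.8 | 5.4% / 5.6% | 6.2% / 6.2% |
| 0.5 | 7.5% / 8.2% | 10.8% / 12.2% |

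With no measurement error, all four cases and all three splits lie between 4.7% and 5.1%. If a second independent factor (0.5 × 0.2) is left out while the 0.5 × 0.4 factor is adjusted for, rejection falls from 28.7% / 34.4% to 7.8% / 8.8%. If both are 0.5 × 0.4, it falls from 46.8% / 54.5% to 16.9% / 19.4%. Adjustment reduces the bias but need not remove it.

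**What adjustment costs in power.** The noncentrality for d = 0.6 is multiplied by √(1 − R²group)/√(1 − R²analyte), where R² is the share of group or analyte variance that the covariates explain. Unadjusted power is 0.80 at 45 per group and 0.88 at 55.

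- Three covariates with an assumed R²group of 0.2 and R²analyte of 0, 0.1 or 0.2: 0.71, 0.76 or 0.80 at 45; 0.80, 0.84 or 0.88 at 55.
- One covariate, with R²group = (imbalance²/4)/(1 + imbalance²/4) and R²analyte = correlation², in the order of the first table: 0.80, 0.80, 0.85 and 0.82 at 45; 0.88, 0.87, 0.91 and 0.89 at 55.

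**The case against.** The strongest reply is that the stated endpoint is a comparison of concentrations, and the planned tests make that comparison. In the illustration the crude levels really do differ by 0.02 to 0.30 SD, so rejecting the crude hypothesis is correct. It misleads only about an adjusted hypothesis that the plan never states. This stands, and the table should not be read as type I error for the literal endpoint. It does not settle the matter. Section 5 presents the levels as a record of exposure before and during pregnancy, and nothing confines conclusions to an unadjusted association. Section 5 is not a causal claim, but it is where a reader would start to make one.

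Second, control by design may sit in the eligibility documents. That cannot be ruled out. What is established is that the plan states none and that no analysis reflects any. Restriction would also deal only with the factors restricted on.

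Third, every imbalance and correlation is assumed, and the results run from negligible to 34.5% by choice of input. The scenarios also show only a spurious difference, although confounding can mask a real one. Both points stand: the size in this study is unknown.

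Fourth, no document says that age, BMI or smoking was recorded. Many extra regressions also raise multiplicity, values below detection and gestational age at sampling. These have to be settled in carrying out the fix; they do not remove the need for it.

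**Conclusion.** The concern holds. As written, the plan can show whether FGR and control women differ in crude levels. Unless the unseen eligibility documents match or restrict on the relevant maternal factors, it cannot show whether a difference is more than maternal imbalance.

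The documents do not allow the effect to be sized for this study. On assumed inputs, rejection with no difference beyond a single factor runs from 5.1% to 29.1% at 45 per group and from 5.1% to 34.5% at 55. This illustrates the mechanism and is not evidence that the study is affected. It should be fixed. Confidence is medium, because the eligibility documents are not available and the literal endpoint is a crude comparison.

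**What to change.** 1. State in the plan any matching or restriction on maternal factors, and reflect matching in the model.
2. Keep the t-test and Mann-Whitney test. Beside them, for each analyte and sample type, fit a regression of concentration (log-transformed where skewed) on group and a short prespecified set of maternal factors that precede the outcome and are on record. Age, BMI and smoking are examples. State in advance how values below detection, gestational age at sampling and the number of comparisons are handled.
3. Report the adjusted difference or ratio with its 95% CI, and base on it any statement beyond a crude difference.
4. Use gestational age at delivery only in a sensitivity analysis, because it may be a consequence of FGR.
5. State that unmeasured or poorly measured factors remain. If the covariates were not recorded, limit the conclusion to an unadjusted association.

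Stratification, or logistic regression with FGR as the outcome, would also serve if chosen in advance.

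The cost is SAP wording and one extra regression per analyte and sample type in SPSS, which the plan already names. Covariates may have to be taken from records and may be unavailable. Little or no power is lost with one covariate in the cases shown. With three, power at 45 per group could fall to 0.71 if they explain none of the analyte variance, which is the case of covariates that are not confounders. The fallback in step 5 costs one sentence.

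### The t-test branch names Student's test with no provision for unequal variances and no stated group sizes; naming Welch's test there is a minor, free improvement

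*Combined protocol and SAP*

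**What the plan says.** Section 2 (Baseline Characteristics) plans two normality tests and then splits the group comparison into two branches. For the first, "the student t-test will be used for variables that have a normal distribution". For the second, "the Mann Whitney U test will be used for variables that have not a normal distribution". The section names no check of equal variances, no unequal-variance version of the t-test and no fallback.

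On numbers, section 1 (Participant Flow, Recruitment Details) says "110 women were enrolled in the study in two groups" and gives no count for either group. Section 2 bases its power calculation on lead levels and a Cohen's d of 0.6, with alpha 0.05 and power 0.80, and reports that the "minimum required sample size was estimated as 45 for each group". No SD is given for any analyte in either group.

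**The concern.** The pooled t-test rests on two assumptions about the data in each group: normality and a common variance. The plan tests the first and is silent on the second. When group sizes and SDs both differ, the pooled standard error is wrong. It is too small if the smaller group is the more variable one, so p-values are too small. It is too large in the reverse case, so power is lost. Confidence intervals from the same test carry the same error. The direction depends on which group is more variable, so a reader cannot correct for it afterwards.

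Silence on the point also leaves room to choose between the pooled and unequal-variance results after the data are seen. Section 3 (Outcome Measures) lists 21 analytes as primary, and any of them judged normal would go through this test.

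**Working it through.** **Inputs from the documents.** Student's t-test for variables judged normal; alpha 0.05; power 0.80; d = 0.6; 45 per group as the estimated minimum; 110 women in total. Sidedness is not stated. Two-sided is inferred, because a one-sided normal approximation would need only 35 per group.

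**Inputs assumed.** The split: if each group has at least 45, it lies between 55/55 and 45/65 (110 − 45 = 65). The SD ratio: 1 to 3.

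**The plan's own figure.** For n per group the noncentrality is d × √(n/2). At n = 45 this is 0.6 × √22.5 = 2.846, and the two-sided pooled t-test has power 0.804. At n = 44 it is 2.814, with power 0.795. So 45 per group reproduces.

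**Hand check of the mechanism, SD ratio 2, split 45/65.** Let the SDs be 2 and 1.

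- *Smaller group more variable.* True variance of the mean difference: 4/45 + 1/65 = 0.1043. Expected pooled variance: (44×4 + 64×1)/108 = 2.222. Variance that the pooled test assigns: 2.222 × (1/45 + 1/65) = 0.0836. Ratio of standard errors: √(0.0836/0.1043) = 0.895. The effective cut-off is 1.960 × 0.895 = 1.755, a two-sided error of about 7.9%.
- *Larger group more variable.* True variance: 4/65 + 1/45 = 0.0838. Expected pooled variance: (64×4 + 44×1)/108 = 2.778. Assigned: 2.778 × (1/45 + 1/65) = 0.1045. Ratio: 1.117. Cut-off: 2.189, an error of about 2.9%.
- *Equal groups, 55/55.* True variance: 4/55 + 1/55 = 0.0909. Assigned: 2.5 × 2/55 = 0.0909. The ratio is 1, so there is essentially no distortion.

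**Exact figures.** Numerical integration over the two sample variances, with normal data and equal means, gives this type I error for the pooled test (smaller group more variable / larger group more variable):

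| Split | SD ratio 1 | 1.25 | 1.5 | 2 | 3 |
|---|---|---|---|---|---|
| 55/55 | 5.0% | 5.0% | 5.0% | 5.1% | 5.2% |
| 50/60 | 5.0% | 5.5% / 4.6% | 5.9% / 4.3% | 6.4% / 3.9% | 7.0% / 3.6% |
| 45/65 | 5.0% | 6.0% / 4.2% | 6.8% / 3.6% | 8.0% / 3.0% | 9.3% / 2.4% |

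Welch's test, with Satterthwaite degrees of freedom, gives 5.0% in every cell. Simulation with 200,000 replicates per scenario agrees: at 45/65 and SD ratio 2 the pooled test gives 7.9% / 2.9%, and at ratio 3 it gives 9.2% / 2.4%.

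**Cost of Welch when SDs are equal (d = 0.6).** Power, pooled against Welch: 0.877 v 0.877 at 55/55, 0.874 v 0.874 at 50/60, and 0.866 v 0.865 at 45/65.

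**The case against.** The strongest reply is that the only allocation the plan describes is one-to-one. It sizes the study with the same minimum for each group, and 110 in two groups fits 55/55, where the pooled test's error is at most about 5.2% even with a threefold SD ratio. This largely stands: under equal groups there is no practical defect. It does not settle the matter, because the split is not stated. Nor would equal enrolment ensure equal numbers in every comparison. The title and section 5 (Limitations and strengths) mention maternal and fetal samples, breast milk, blood, urine and hair, and the plan does not say that every woman supplies each of them.

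Second, an unstated split does no harm by itself. With equal SDs the pooled test holds 5% at any split. That is correct, and the concern needs both inequalities together.

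Third, the plan never uses the words pooled or equal variance. That is so. The equal-variance version is the usual meaning of the name, but it remains a reading.

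Fourth, the effect is small beside the 21 primary analytes tested at an unadjusted 0.05. If those tests were independent, the chance of at least one false positive would be 1 − 0.95^21, about 66%, and Welch's test would not materially change that. This also stands and limits the priority of the point. It is not a reason to decline a free correction.

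**Conclusion.** The point holds as a minor one. The plan names Student's t-test, makes no provision for unequal variances and does not give the group sizes. If both sizes and SDs differ, the 5% error moves to roughly 7% to 8% or 3% to 4% at 45/65 with SD ratios of 1.5 to 2, and by less at 50/60. These figures rest on normal data, a two-sided test, and a split and SD ratio that are assumed.

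Three stronger readings should be avoided.

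- A reader might infer that the plan's type I error is about 9% or 2%. Within splits that keep 45 per group, those values need both the most unequal one and an SD ratio near 3, and the documents state neither.
- A reader might infer that all 21 primary analytes are affected. Only those judged normal reach the t-test, and the documents do not indicate how many will.
- A reader might take 45 per group as guaranteed. It is an estimated minimum sample size, not an enrolment rule, so 45/65 is a limit conditional on meeting it.

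The case for change rests on its negligible cost, not on large demonstrated harm.

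**What to change.** In section 2, replace Student's t-test with Welch's unequal-variance t-test for the variables judged normal, and take any reported mean difference and 95% confidence interval from that test. Leave the Mann-Whitney U branch as planned. State the number of women in each group, and report the number analysed per group for each comparison.

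The cost is a few words in the analysis plan. It needs no extra participants or measurements, and at the plan's effect size the power loss under equal SDs is at most about 0.1 percentage point.

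### ROC cut-offs will be chosen on the same 110 women with no internal validation, so any sensitivity and specificity quoted at those cut-offs will on average be too favourable

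*Combined protocol and SAP*

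**What the plan says.** The statistical methods stand in Section 2 (Baseline Characteristics) of the combined protocol and SAP. One sentence there covers ROC analysis: "The ROC analysis will be applied for the determination of cut-off point for variables". It does not name the criterion for choosing a cut-off, list the variables, or say which accuracy measures will be reported.

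On the data available, Section 1 (Participant Flow) says "110 women were enrolled in the study in two groups", without giving the split. On size, Section 2 says "minimum required sample size was estimated as 45 for each group". That figure is for a difference in lead levels at d = 0.6 with 80% power, not for ROC accuracy. On tools, it says "SPSS for Windows 22.0 and Medcalc programs will be used for statistical analysis". No section mentions a pre-specified threshold, a second sample, cross-validation, resampling or correction for optimism.

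Sections 3 and 4 make the primary outcome the between-group comparison of 21 analyte concentrations. ROC analysis is not listed as a primary, secondary or tertiary outcome.

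**The concern.** A cut-off chosen to do well on a sample exploits the chance features of that sample. Its sensitivity and specificity, counted in the same women, are therefore higher on average than they would be in new women from the same population.

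Determining a cut-off is the stated purpose of the ROC step. If a threshold is published with its accuracy, readers will take the figures as how well the analyte separates growth-restricted pregnancies from controls. An ordinary confidence interval does not repair this, because it is centred on the optimistic estimate and treats the cut-off as if it had been fixed beforehand.

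**Working it through.** **Inputs from the document.** 110 women in two groups; minimum 45 per group; d = 0.6; alpha 0.05; power 0.80.

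**Assumptions not in the document.** A 55/55 split; normal data with equal variance; three possible cut-off rules.

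**Step 1: the plan's own figure.** The normal approximation for a two-sided test gives n = 2 × (1.960 + 0.842)² / 0.6² = 43.6, so 44 per group. The exact two-sample t calculation gives 44.59, so 45. The stated 45 is reproduced (power 0.804 at 45 per group, 0.877 at 55). It does not bear on ROC accuracy, but it supplies a plausible effect size.

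**Step 2: formulas.** Let controls be N(0, 1) and cases N(d, 1), with a positive result above cut-off c. The true values at c are:

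- sensitivity = 1 − Φ(c − d)
- specificity = Φ(c)
- J = sensitivity + specificity − 1

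The best achievable J is at c = d/2. For d = 0.6 it is 2Φ(0.3) − 1 = 0.236. The apparent values are the proportions counted in the sample that chose c. Optimism is apparent minus true J at that same c; half of it is the average excess in each of sensitivity and specificity.

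**Step 3: simulation, 10,000 datasets per row, 55/55, d = 0.6.**

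| Cut-off rule | Apparent J | True J | Optimism in J | Per measure |
|---|---|---|---|---|
| Youden (maximum J) | 0.309 | 0.217 | 0.092 | 4.6 points |
| Closest to corner | 0.293 | 0.231 | 0.062 | 3.1 points |
| Specificity at least 90% | 0.164 | 0.143 | 0.021 | 1.0 point |

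The bias was upward for both measures under every rule. Absolute levels of sensitivity and specificity under Youden are not quoted, because they move by several points with the handling of tied cut-offs. The gap is stable.

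**Step 4: range under Youden, direction fixed in advance unless stated.**

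- Split 45 cases/65 controls or 65/45, d = 0.6: optimism in J 0.094 and 0.095.
- 45/45, d = 0.6 (direction chosen from the data): 0.318 − 0.213 = 0.105.
- 55/55, d = 0.3: 0.205 − 0.102 = 0.103.
- 55/55, d = 1.0: 0.444 − 0.364 = 0.080.
- 55/55, no true difference: 0.110, or 0.155 if the direction is also chosen from the data.

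These figures depend only on ranks, so they also hold for skewed analytes that become normal with equal variance after a monotone transformation.

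**Step 5: does an ordinary interval cover it?** Under Youden at 55/55 and d = 0.6, 95% Wilson intervals contained the true sensitivity in 90.7% of datasets and the true specificity in 91.1%. A Wald interval for J contained the true value in 83.2%. Nearly all misses lay too high.

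**Step 6: does the bootstrap correct it?** With the Youden selection repeated in each resample (55/55, d = 0.6), mean J fell from 0.306 to 0.243 against a true 0.214. The share of bias removed is (0.306 − 0.243) / (0.306 − 0.214) = 0.063 / 0.092 = 68%. Other runs, varying d, sample size and handling of direction, gave 64% to 80%.

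**The case against.** The strongest reply is that this is one descriptive sentence in a short case-control plan. The document does not promise to report sensitivity or specificity, and it gives no diagnostic or screening use for a threshold. The bias is also smaller than the sampling error: with 55 per group and a proportion near 0.65, one standard error is √(0.65 × 0.35 / 55) = 0.064, or 6.4 points, against at most about 4.6 here. The size also rests on an unstated criterion, and the bootstrap removes only part of the bias.

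Much of this stands. The point is conditional on accuracy being reported, the size must be given as a range, and the criterion has to be named first because a bootstrap cannot repeat a selection rule that has not been stated. It does not remove the point. A cut-off is hard to interpret without its accuracy. Sampling error goes either way and is shown by an interval, whereas this bias runs upward on average: under Youden, apparent J exceeded true J in about 90% of datasets.

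A reader might infer two stronger things. One is that the study's main result is compromised. It is not, since the primary comparison uses the t-test or Mann-Whitney test and no cut-off. The other is that the best-looking of the 21 analytes will be put forward, adding selection bias. That would add optimism, but the plan does not say it will be done.

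**Conclusion.** The point holds, as a limited weakness in a supplementary analysis. Following the ROC sentence as written gives sensitivity and specificity that are too favourable on average, by roughly 1 to 5 points each at 55/55 and d = 0.6. The upper end should not be read as the size of the problem, because it requires a Youden rule that the plan never states. Under Youden the overstatement of J is 0.092 on a true 0.217, or about 42% in relative terms; with specificity held at 90% or more it is close to negligible. The direction is the same for every rule, split and effect size tried. The split and the equal-variance normal shape (possibly after transformation) are assumptions.

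**What to change.** Amend the ROC sentence in Section 2 to:

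1. Name the cut-off criterion and the variables to be given a ROC curve.
2. Report bootstrap optimism-corrected sensitivity, specificity and Youden index (for example, 1,000 resamples). Each resample should repeat the named selection rule and any data-driven choice of direction or analyte.
3. Report the AUC with a 95% confidence interval for every variable examined.
4. Label the cut-offs exploratory pending external validation. This is needed even with item 2, because under Youden the bootstrap removes only about two-thirds to four-fifths of the bias.

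A bootstrap confidence interval for the cut-off itself is optional.

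The cost is a short amendment and a little more analysis of data already being collected, possibly with a script outside the two named packages. The reported accuracy will look less favourable.
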